2.4 HANDLING OF MISSING DATA

Missing data will not be imputed for descriptive statistical summaries in safety or efficacy analyses.

For the PGI-I score, missing data at Day 42 will be considered as failure in analysis.

Dates missing the day or both day and month of the year will adhere to the following conventions to classify TEAE and to classify prior/concomitant medications.

- A medication with a completely missing start date will be considered a prior medication. A medication with a completely missing stop date will be considered a concomitant medication.
- If complete AE onset date is missing and AE end date is on or after the first dose date then it will be counted as a treatment emergent AE (TEAE) for the study. If complete AE onset date is missing and AE end date is before the first dose date then it will be counted as a not treatment emergent AE (TEAE) for the study.
- If an AE or a medication has a partial missing start or stop date, the following rules will be used for imputation:
 - If year is present but month and day are missing, impute start date as January 1 of that year or first dose date if the year is the same as the year of first dose date and impute stop date as December 31 of that year.
 - If year and day are present but month is missing, impute start month as January or the month of the first dose date if the year and day is the same as the year and day of first dose date and impute stop month as December.
 - If year and month are present but day is missing, impute start date as first day of that month or first dose date if the year and month are the same as the year and month of first dose date and impute stop date as last day of that month.

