Timing: Non-serious adverse events will be reported from the initial treatment with study drug through the completion of the study or a follow-up phone call 28 days following the last dose of study drug for subjects who are randomized and terminate early from the trial. All ongoing adverse events related to study drug (i.e., FCM or Placebo) should be followed until they are no longer related, have taken a confounding medication or return to baseline grade.

Relationship (Causality): The Investigator will be asked to document his/her opinion of the relationship of the event to the study drug_as follows:

- NONE There is *no* evidence of any causal relationship.
- UNLIKELY There is *little* evidence to suggest there is a causal relationship. There is *another reasonable explanation* for the event (e.g., the subject's clinical condition, other concomitant treatments).
- POSSIBLE There is *some* evidence to suggest a causal relationship (i.e. there is a reasonable possibility that the adverse experience may have been caused by the agent). However, the influence of *other factors may have contributed* to the event (e.g., the subject's clinical condition, other concomitant events).
- PROBABLE There *is evidence* to suggest a causal relationship, and the influence of other factors is *unlikely*.

For the purposes of this trial, "study drug" is defined as: Injectafer® or Placebo (Normal Sterile Saline).

7.2 **Reporting of Adverse Events**

Adverse experiences will be elicited by nonspecific questions such as "Have you noticed any problems?" Subjects will be encouraged to report adverse events at the onset. Any adverse experience spontaneously reported by, elicited from the subject or observed by the physician or study staff shall be recorded on the appropriate Adverse Event page of the CRF. The Investigator will record the date and time of onset, severity, the relationship to study medication, the date and time of resolution (or the fact that the event is still continuing), the action taken, and the outcome of the adverse experience on the Adverse Event page of the CRF. Whenever possible, the Investigator should group together, into a single term, signs and symptoms which constitute a single diagnosis. For example, cough, rhinitis and sneezing might be grouped together as "upper respiratory infection."

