7.1 ADVERSE EVENTS

Adverse events (AEs) will be coded by System Organ Class (SOC) and Preferred Term (PT) using the Medical Dictionary for Regulatory Activities (MedDRA®, version 24.0 or higher). The verbatim term will be included in the AE listings.

A treatment-emergent adverse event (TEAE) is defined as an AE that occurs or worsens on or after the first dose of study drug in Phase I. Only TEAEs will be included in summary tables by treatment group (for Phase I only) for each phase. For AEs occurring on the first dosing day, if the start time cannot be ascertained, the event will be counted as treatment emergent. All AEs, treatment emergent or otherwise, will be presented in subject data listings.

The incidence of TEAEs will be summarized as the number (percentage) of subjects with TEAEs within SOC and PT by treatment group (for Phase I only) for each phase. Subjects who report the same PT on multiple occasions will be counted once for the PT: under the highest severity (severe > moderate > mild) when summarized by severity and under the closest relationship (probably related > possibly related > unlikely related > none) to study drug when summarized by relationship. If a subject reports multiple PT for a SOC, the subject will be counted only once for that SOC. Events with unknown severity or relationship will be counted as unknown.

TEAEs will be summarized as below.

- An overview table, including number of subjects with
 - TEAEs
 - serious AEs (SAEs)
 - study drug related TEAEs
 - study drug related SAEs
 - TEAEs by severity
 - TEAE of special interest (AESI)
 - TEAEs leading to study discontinuation
 - TEAEs leading to death
- TEAE by SOC and PT
- TEAE by SOC, PT, and Severity
- Study drug related TEAEs by SOC, PT
- SAEs by SOC and PT
- TEAEs leading to study discontinuation by SOC and PT

All TEAE tables will be sorted by SOC and PT in decreasing frequency of the number and percentage of subjects in the treatment group.

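### SAP 2.4 dates an adverse event with a missing start month to January, which usually drops a same-year post-dose event from the TEAE tables; the rule is wrong as written, but the expected effect is small

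*SAP*

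**What the plan says.** SAP 2.4 has three rules for a partial AE start date.

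- Month missing, year and day known: "impute start month as January or the month of the first dose date if the year and day is the same" as those of the first dose.
- Day missing, year and month known: "impute start date as first day of that month or first dose date if the year and month are the same" as those of the first dose.
- Year only: "impute start date as January 1 of that year or first dose date if the year is the same" as that of the first dose.

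A fourth rule covers an onset date that is wholly absent: "If complete AE onset date is missing and AE end date is on or after the first dose date then it will be counted" as treatment-emergent. None of the three partial-date rules looks at the end date.

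The lead-in gives the purpose: "Dates missing the day or both day and month of the year will adhere to the following conventions to classify TEAE" and prior or concomitant medication status. Assignment of an AE to a study phase is not mentioned there, and SAP 7.1 gives no rule for it.

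SAP 7.1 defines a treatment-emergent AE (TEAE) as "an AE that occurs or worsens on or after the first dose of study drug in Phase I" and adds: "Only TEAEs will be included in summary tables by treatment group (for Phase I only) for each phase". It also keeps every AE in the subject listings, whether or not it is treatment-emergent.

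On collection, Protocol 7.1 (Timing) states: "Non-serious adverse events will be reported from the initial treatment with study drug through the completion of the study". Protocol 7.3 starts SAE reporting on the day of first treatment. Protocol 7.2 asks the investigator for the date and time of onset.

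**The concern.** An imputation rule for AE dates should not move an event across the first dose unless the known facts put it there. The month-missing rule does so by default: it picks the earliest month of the year and falls back to the first-dose month only when the day number happens to match.

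The section also becomes inconsistent. Take an AE that ended after first dose. If nothing is known about its onset, it counts as a TEAE. If the year and day of onset are known, it may not. Having more information gives a worse classification.

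Safety is part of the primary objective (SAP 1.1.1). Because the study ended early, SAP 9 drops the model-based testing, so descriptive tables carry most of the report. At the planned 35 subjects per arm, one subject is 1/35 = 2.9 percentage points in an incidence table.

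**Working it through.** The plan gives no figure on this point, so there is none to reproduce. I applied the rules as written.

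**Inputs.** The three partial-date rules come from SAP 2.4 and the TEAE definition from SAP 7.1. Three assumptions are mine: first-dose dates are even over the 365 days of one calendar year, onsets are even over the 365 days starting at first dose, and the missing pattern is unrelated to the date.

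**Month-missing rule as a formula.** Let the first dose fall on day *d* of month *m* in year *Y*, and let the AE have day *a* in year *A*.
- If *A* = *Y* and *a* = *d*, the imputed date is *a*/*m*/*A*.
- Otherwise it is *a*/January/*A*.
- The event is not treatment-emergent if the imputed date is before the first dose.

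**One subject, by hand.** First dose 15 June 2018.
- True onset 20 June, month missing: imputed 20 January 2018, not treatment-emergent.
- True onset 10 August, month missing: imputed 10 January 2018, not treatment-emergent.
- From 15 June to 31 December there are 200 possible onset days. Only the seven 15ths (June to December) keep TEAE status. The other 193 lose it: 193/200 = 96.5%.

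**All first-dose days.**
- Pairs of first-dose day and onset day: 365 × 365 = 133,225.
- Pairs with onset in the dosing year: 365 × 366 / 2 = 66,795.
- Pairs in which the imputed date precedes first dose, counted by applying the rule to every pair: 59,078, all in the dosing year. A January date in the following year can never precede first dose.
- Same-year share: 59,078 / 66,795 = 88.4%.
- Share over the full 365 days: 59,078 / 133,225 = 44.3%.

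By phase of true onset, over all calendar years and with Phase II Day 0 set 42 to 52 days after Phase I Day 0, the share losing TEAE status is 85% for Phase I, 73–77% for Phase II and 32–33% for Phase III.

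**The other two rules.** On the same grid, the day-missing and year-only rules take TEAE status from 0% of post-dose events. If the known parts match the first dose, the date becomes the first dose date. If they do not, the first of a later month, or 1 January of a later year, is already after first dose.

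**Consistency.** Take the 20 June event again and let it end on 5 July 2018. With no onset date at all, the end date makes it a TEAE. With day 20 and year 2018 known, it is not a TEAE. Protocol 7.1 collects non-serious AEs only from first treatment, so a recorded event is expected to be post-dose in either case.

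**The case against.** **The pattern is rare.** A date with a day and year but no month is unusual, and Protocol 7.2 asks for the full onset date and time. The SAP 2.4 lead-in does not even name this pattern, although a bullet covers it. The documents give no count of partial dates, so every percentage above is a share of an unknown and probably small number. This stands and limits the size of the point.

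**Nothing leaves the report entirely.** Dropped events stay in the listings, and SAP 7.1.2 lists SAEs, deaths and AEs leading to discontinuation. This stands too, but the tables would still be wrong.

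**A reader might infer that the rules also move open-label FCM events into Phase I, including the placebo column.** If phase were assigned from the imputed date, 35% of day-missing and 94% of year-only Phase II onsets would fall in Phase I under uniform dates. The SAP does not say that phase is assigned this way, and its lead-in limits the conventions to TEAE and medication status. Phase could come from the visit at which the AE was reported; in Phase II these are Days 0, 7, 28 and 42. What stands is that the assignment rule is not stated.

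**A reader might infer that the errors make FCM look safer.** The month-missing rule ignores treatment and can drop events from either arm. Any moved Phase II event would land in the subject's own Phase I arm, and non-responders from both arms can enter Phase II. As a rough guide, take the planned CGI-I rates of 50% and 15% as response rates, with equal arms and no laboratory criteria. The FCM arm then supplies 50 / (50 + 85) = 37% of entrants, and their moved events would count against FCM.

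**Conclusion.** The month-missing rule is wrong as written. It classes most same-year post-dose AEs with that pattern as not treatment-emergent (about 88%, or 44% over 365 days), with no regard to the end date, and it contradicts both the rule for a wholly missing onset and the AE reporting window. That it can drop post-dose events follows from the text alone; the percentages rest on uniform dates.

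The expected effect on the tables is small. The documents do not support the wider readings: only this one of the three rules drops TEAEs, a shift of events between phases depends on an assignment method that the SAP does not state, and no bias towards either arm is shown.

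One caveat: the SAP cites a protocol dated 4 September 2019, while the protocol supplied carries April 2016 dates. I assume that the AE reporting window did not change.

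**What to change.** Replace the month-missing rule for AEs in SAP 2.4 with wording such as:

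> An AE with a partial start date is treatment-emergent unless its known date parts or its end date show that it began before the first dose in Phase I. Where the known parts allow it, the imputed date is not earlier than the first dose date.

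Add to SAP 7.1 that an AE is assigned to a phase from the known parts of its start date and, where these are ambiguous, from the visit at which it was first reported, not from the imputed date.

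Do not solve the phase question by imputing the latest compatible dose date. For ongoing Phase I AEs in subjects who enter Phase II, I applied that alternative on the same uniform grid. It moves 28% of day-missing events (Phase II Day 0 at 52 days) to 35% (at 42 days), and 93–94% of year-only events, out of the randomised comparison and into open-label FCM.

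Keep the present rules for medications. The cost is one SAP paragraph and a small programming change. The downside is that a few AEs that began before dosing may be counted as TEAEs.

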2.5 ANALYSIS SOFTWARE

All summaries and statistical analyses will be generated using SAS® version 9.4 or higher.

3. STUDY SUBJECTS

3.1 DISPOSITION OF SUBJECTS

Disposition will be summarized for all randomized subjects.

The disposition will include the following:

- Subjects who are randomized (for Phase I only)
- Subjects who are in Safety Population
- Subjects who are in ITT population
- Subjects who complete the study
- Subjects who discontinue the study

The number and percent of subjects will be summarized for each reason for premature discontinuation.

A listing of dispositions will be provided for all subjects.

3.2 PROTOCOL DEVIATIONS

The clinical team will identify deviations and the deviations will be identified and classified into types in the database. The number and percent of subjects will be presented. Summaries will include type of deviation by treatment phase, treatment group (for Phase I only).

A subject data listing of protocol deviations will be provided.

4. DEMOGRAPHICS AND BASELINE CHARACTERISTICS

4.1 DEMOGRAPHICS AND BASELINE CHARACTERISTICS

Baseline characteristics (e.g., sex, age, race, ethnicity, height and weight) will be summarized with descriptive statistics or frequency counts by treatment phase, treatment group (for Phase I only) and overall for the Safety population.

4.2 MEDICAL HISTORY

Medical history will be collected prior to the treatment Phase I. Data will be coded with the Medical Dictionary for Regulatory Activities (MedDRA) Terminology. Events will be coded to System Organ Class (SOC) and preferred term (PT) using MedDRA Version 24.0 or higher. The number and percent of subjects with clinically significant medical history at screening will be summarized by system organ class (SOC) and preferred term (PT) by treatment phase, treatment group (for phase I only) and overall for safety Population.

5. STUDY DRUG AND EXPOSURE

5.1 TREATMENT COMPLIANCE AND EXTENT OF EXPOSURE

Treatment compliance will not be summarized, as each subject will be treated in an inpatient setting to receive a single dose of study drug on Day 0 and Day 7 of Phase I or II or a single dose during any time before week 46 of Phase III.

The number (percentage) of subjects who received IV injections of study drug will be summarized by treatment phase, treatment group (for Phase I only) and overall for safety population. The number (percentage) of subjects who received additional IV injection of study drug in Phase III will be summarized for Phase III safety population.

5.2 PRIOR AND CONCOMITANT THERAPY

Prior only medications are defined as medications that stopped prior to the first dose of study drug in Phase I. Concomitant only medications are defined as medications (other than the study drug) taken on or after the first dose of the study drug in Phase I during the study. Medications started before the first dose of study drug in Phase I and continuing at the time of the first dose of study drug are considered as both prior and concomitant medication.

All investigator terms for medications recorded on the CRF will be coded using the World Health Organization (WHO) Anatomical Therapeutic Chemical (ATC) drug dictionary (Version WHO Drug Dictionary Enhanced, WHO DDE March 2021 or higher). The number (percentage) of subjects who took prior medications will be summarized by treatment group in Phase I and overall for Treatment Phase I safety population. Prior general medications and iron/RLS therapies will be summarized separately. The number (percentage) of subjects who took concomitant medications will be summarized by treatment phase, treatment group (for Phase I only) and overall for safety population.

6. EFFICACY ANALYSES

All efficacy analyses will be based on the Safety Population for each phase accordingly.

Statistical testing for treatment effect:

- Phase I, II and III: no formal statistical testing will be performed. Data will be reported via descriptive statistics only.

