1.2.2 Secondary Efficacy Endpoint(s)

Treatment Phase I and Phase II:

- Change in IRLSS score from Baseline to Day 42. (Treatment Phase I and II)
- IRLSS score change from Baseline (For Phase II the “Baseline” is established on Day 42 of Phase I) compared to Day 42 of Treatment Phase II.
- CGI-I and PGI-I at each visit and percentage of subjects who are much or very much improved at Day 42. (Treatment Phase I and II)
- Change in sleep quality (MOS Sleep) from Baseline to Day 42. (Treatment Phase I and II)
- Estimate the proportion of treatment non-responders in Phase I who respond to FCM in Phase II for each randomized treatment group. (Phase II only)
- Change in substantia nigra iron index from Baseline to Day 42. The index will be determined using measures of MRI relaxation rate (R2*) or Quantitative Susceptibility Mapping (QSM). (Treatment Phase I and II)
- Change in iron index (R2* or QSM) for thalamus and motor cortex from Baseline to Day 42. (Treatment Phase I and II).

Treatment Phase III:

- Change in IRLSS total score from baseline to each scheduled visit.
- Number (and percentage) of subjects who remain in the study to Week 52.

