2.2 DEFINITIONS OF ANALYSIS POPULATIONS (ANALYSIS SETS)**2.2.1 ITT Population**

ITT population includes all the subjects who were randomized.

Summaries for ITT population will be based on the treatment group to which they were randomized.

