2.2.2 Safety Population

Safety population includes all the subjects who were randomized and received at least one dose of study medication.

Summaries for safety population will be based on the actual treatment they received.

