6.1 PRIMARY EFFICACY ANALYSIS

6.1.1 Phase I and Phase II: Change in IRLSS total score from baseline to Day 42

The actual value of IRLSS total score on baseline and Day 42, and change from baseline to Day 42 will be summarized via descriptive statistics by treatment group for each treatment phase.

A subject data listing of IRLSS total score for each visit will be provided.

6.1.2 Phase I and Phase II: Percentage of subjects who are much or very much improved at Day 42 as measured by the CGI-I

The number (percentage) of subjects who are rated as much or very much improved with the CGI-I on Day 42 will be summarized by treatment group (for Phase I only) for each treatment phase. The denominator should be the Phase I Safety population for each treatment group in Phase I. For Phase II, the denominator is the Safety population in Phase II.

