6.2 SECONDARY EFFICACY ANALYSES

6.2.1 Phase I and II: Change in IRLSS total score from baseline to Day 42 (Non-responders in Phase I Placebo group)

The change is defined as IRLSS total score at Day 42 minus IRLSS total score at baseline in each phase. The number of subjects, mean, median, standard deviation, minimum (min) and maximum (max) for the observed values, and change from baseline will be reported in summary table.

6.2.2 Phase I and II: Change in IRLSS total score from baseline to Day 42 (Non-responders in Phase I FCM group)

IRLSS total score from baseline to Day 42 between Phase I and Phase II will be summarized. The change is defined as IRLSS total score at Day 42 minus IRLSS total score at baseline in each phase. The number of subjects, mean, median, standard deviation, minimum (min) and maximum (max) for the observed values, and change from baseline will be reported in summary table.

6.2.3 Phase I and Phase II: CGI-I and PGI-I score at Day 42

The number (percentage) of subjects of each category will be summarized for CGI-I and PGI-I, separately.

6.2.4 Phase I and Phase II: Percentage of subjects who are much or very much improved at Day 42 as measured by the PGI-I

The number (percentage) of subjects who are rated as much or very much improved with the PGI-I on Day 42 will be summarized by treatment group (for Phase I only) for each treatment phase.

6.2.5 Phase I and Phase II: Change in sleep quality measured by MOS from baseline to Day 42

The actual value of MOS score on baseline and Day 42, and change from baseline to Day 42 will be summarized via descriptive statistics by treatment group (for Phase I only) for each treatment phase.

6.2.6 Phase I and Phase II: Number (percentage) of treatment non-responders at Day 42 of Phase I who respond to FCM in Phase II

The number (percentage) of treatment non-responders at Day 42 in Phase I who are turned into responders in Phase II, and the treatment responders of each phase, will be summarized by treatment group, separately. For Phase I, treatment differences in percentage will be assessed with the chi-square test, p-values will be presented. The subjects who missing responder/non-responder classification will be considered as non-responder.

6.2.7 Phase I and Phase II: Number (percentage) of treatment responders at Day 42

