The number (percentage) of treatment responders at Day 42 of Phase I and Phase II will be summarized by treatment group in Phase I, separately. The subjects who missing responder/non-responder classification will be considered as non-responder.

6.2.8 Phase I and Phase II: Change in substantia nigra iron index from baseline to Day 42

The actual value of substantia nigra iron index on baseline and Day 42, and change from baseline to Day 42 will be summarized via descriptive statistics by treatment group (for Phase I only) for each treatment phase.

Substantia nigra iron index will be measured using MRI relaxation rate (R2*) or QSM.

6.2.9 Phase I and Phase II: Change in thalamus and motor cortex iron index from baseline to Day 42

The actual value of thalamus and motor cortex iron index on baseline and Day 42, and change from baseline to Day 42 will be summarized via descriptive statistics by treatment group (for Phase I only) for each treatment phase, separately.

Iron index will be measured using MRI relaxation rate (R2*) or QSM.

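### Phase I efficacy is grouped by treatment received, while the as-randomised ITT population the SAP defines is used only for a disposition count

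*SAP*

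**What the plan says.** Section 6 of the SAP sets one population for every efficacy table: "All efficacy analyses will be based on the Safety Population for each phase accordingly". Section 6.1.2 repeats this for the CGI-I co-primary: "The denominator should be the Phase I Safety population for each treatment group in Phase I".

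The grouping rule for that population is in section 2.2.2: "Summaries for safety population will be based on the actual treatment they received". Membership requires randomisation and at least one dose.

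Section 2.2.1 defines a second population, all randomised subjects, with the opposite rule: "Summaries for ITT population will be based on the treatment group to which they were randomized". After its definition, this population appears only as a line in the disposition list of section 3.1, "Subjects who are in ITT population". No efficacy table uses it.

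Three other places bear on the point:

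- The Phase II secondary endpoint in section 1.2.2 is stated by randomised arm: "Estimate the proportion of treatment non-responders in Phase I who respond to FCM in Phase II for each randomized treatment group".
- Section 6.2.7 says: "The number (percentage) of treatment responders at Day 42 of Phase I and Phase II will be summarized by treatment group in Phase I". It does not say whether the group is the assigned or the received one, so the general rule of sections 6 and 2.2.2 applies.
- Section 6.2.6 keeps a between-arm test: "For Phase I, treatment differences in percentage will be assessed with the chi-square test, p-values will be presented". Section 6 says that no phase will be formally tested, and item 1 of section 9 gives early termination as the reason.

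**The concern.** Grouping by treatment received is the normal choice for safety. For efficacy it gives up the protection of randomisation in the one situation where the choice matters, a dosing error. Phase I is the only part of this trial with a randomised control, so the FCM and placebo columns there will be read as the randomised contrast even if no test is attached.

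Under the current text, a subject assigned to one arm and dosed with the other product moves to the other column in the IRLSS change (6.1.1), the CGI-I percentage (6.1.2), the responder counts (6.2.7) and the chi-square (6.2.6). The endpoint in 1.2.2 asks for results by randomised arm, and as-treated grouping does not guarantee that.

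The SAP also gives no rule for a subject who received different products on Day 0 and Day 7, so actual treatment is not fully defined. Grouping as randomised makes that question irrelevant to Phase I efficacy.

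**Working it through.** **The plan's own figures.** With 35 per arm, two-sided alpha 0.05 (SAP 1.3.3 states alpha for the t-test; it is assumed for the chi-square):

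- CGI-I 50% v 15%: power is 0.896 by the normal approximation. Exact enumeration of the Pearson test gives 0.903, or 0.852 with continuity correction. The stated bound is above 85%.
- IRLSS difference 5.0, SD 7.3: power is 0.817 by the normal approximation and 0.806 by the noncentral t. The stated bound is above 80%.

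Both stated bounds are met, and neither depends on the grouping rule.

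**Effect of one misdosed subject at the planned size.** Inputs from SAP 1.3.3: 35 per arm, 50% and 15%. These give 17.5 and 5.25 expected responders, taken as 17 and 5. Misdosing is assumed complete, so the subject is classed in the other arm.

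Difference = responders/n (FCM) − responders/n (placebo).

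| Case | FCM | Placebo | Difference (points) |
|---|---|---|---|
| As randomised | 17/35 | 5/35 | 34.3 |
| FCM responder counted as placebo | 16/34 | 6/36 | 30.4 |
| FCM non-responder counted as placebo | 17/34 | 5/36 | 36.1 |
| Placebo responder counted as FCM | 18/36 | 4/34 | 38.2 |
| Placebo non-responder counted as FCM | 17/36 | 5/34 | 32.5 |
| One undosed FCM non-responder dropped | 17/34 | 5/35 | 35.7 |

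The shift from one misdosed subject is about 2 to 4 points, in either direction.

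**Effect on the retained p-value.** The number of subjects at termination is not in the documents, so a range is shown. The planned CGI-I rates stand in for the responder rates; this is an assumption, because the responder definition in SAP 1.3.1 also counts an IRLSS of 10 or less.

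Pearson chi-square without continuity correction: χ² = N(ad − bc)² / [(a+b)(c+d)(a+c)(b+d)]. For 10/20 v 3/20: 40 × (10×17 − 10×3)² / (20×20×13×27) = 784,000/140,400 = 5.58, p = 0.018.

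| Assumed 20 per arm | FCM | Placebo | Difference (points) | p |
|---|---|---|---|---|
| As randomised | 10/20 | 3/20 | 35.0 | 0.018 |
| FCM responder moved | 9/19 | 4/21 | 28.3 | 0.056 |
| FCM non-responder moved | 10/19 | 3/21 | 38.3 | 0.010 |
| Placebo responder moved | 11/21 | 2/19 | 41.9 | 0.005 |
| Placebo non-responder moved | 10/21 | 3/19 | 31.8 | 0.032 |

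The same four moves at other sizes:

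- 25 per arm, 12 v 4: p goes from 0.015 to between 0.0045 and 0.044.
- 35 per arm, 17 v 5: p goes from 0.002 to between 0.0006 and 0.006.

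**The case against.** The strongest reply is that nothing is shown to have happened. The documents report no misdosed subject. Protocol 5.2, 5.2.1.1 and 6.4.1 describe controls that make one unlikely: assignment through the IRT system, unblinded staff who look up the allocation and give the drug, and a separate dosing record at each dose. After early termination the co-primary summaries are descriptive, so no primary hypothesis test is at risk. A shift of 2 to 4 points at 35 per arm is small beside the standard error of the difference, √(0.486×0.514/35 + 0.143×0.857/35) = 10.3 points. Whether the p-value crosses 0.05 depends on the assumed size: in these examples it does at 20 per arm and does not at 25 or 35. The illustrations also assume complete misdosing, while Phase I has two doses.

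The departure from the protocol cannot be established either. The Phase I Full Analysis Set in Protocol 8.2 also required treatment and states no grouping rule. The SAP follows a protocol dated 4 September 2019, whereas the one supplied carries April 2016 dates.

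These points limit the size of the problem and its likelihood. They do not remove it. A grouping rule should be right before anyone knows whether it matters, and descriptive arm columns will still be read as the randomised comparison. Leaving out undosed subjects is not the complaint, since the supplied protocol does so too. The conflict between 6.2.6 and section 6 is a separate inconsistency that stands even if every subject was dosed as assigned.

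**Conclusion.** The point holds. The text assigns all Phase I efficacy to an as-treated population and leaves the as-randomised one unused for efficacy. The numerical effect is zero if no subject was misdosed or left undosed. With one completely misdosed subject, the Phase I CGI-I difference moves from 34.3 points to between 30.4 and 38.2 at the planned size and rates. The 6.2.6 p-value can move from 0.018 to between 0.005 and 0.056 at an assumed 20 per arm; the actual size at termination is not given. It should be corrected because the rule is wrong for a randomised comparison and the correction is nearly free, not because a distortion has been shown.

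**What to change.** 1. Change section 6 so that Phase I efficacy uses the ITT population, grouped as randomised. If the sponsor prefers to keep the present membership, use all randomised and dosed subjects, still grouped as randomised.
2. Use the same Phase I denominators in 6.1.2, 6.2.4, 6.2.6 and 6.2.7. This concerns Phase I rows only.
3. Keep the as-treated Safety Population for section 7, and Safety membership for Phases II and III. Split the Phase II results in 6.2.1, 6.2.2 and 6.2.6 by Phase I arm as randomised, which also satisfies the endpoint in 1.2.2.
4. Reconcile the chi-square in 6.2.6 with sections 6 and 9: remove it, or name it in section 6 as the single exception.
5. List the efficacy population in section 9 if it differs from the 4 September 2019 protocol.

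The cost is SAP wording and a population flag that 2.2.1 already defines; no new data are needed. The drawback of full ITT is that an undosed subject counts as a CGI-I failure: for one undosed FCM subject at 35 per arm, 34.3 points (17/35 v 5/35) instead of 35.7 (17/34 v 5/35). The randomised-and-dosed option avoids this, and if nobody was misdosed it changes no result.
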